CONN creates subject-specific ROI files and registers them to the subject space. 99 ROIs will be used as the seeds of interest for whole-brain subject-specific ROI-ROI connectivity analyses.

**Power Analysis:** Power analysis for drinks consumed per day during the last three weeks of treatment were determined using data for the placebo and zonisamide groups from our previous study (Knapp et al., 2015). A power value of 0.9 was found for a group size of 40, with alpha=0.05, and with an effect size of 0.74. In our previous study of ZON approximately 20% of subjects dropped out before week 12 of the study. Consequently, we will randomize 50 subjects per group to reach a target of 40 subjects in week 12 of the present study. Based on data reported by Rubio et al. (2009) for errors of commission on the CPT, a measure of impulsivity, a power value of 0.97 would be obtained for an alpha value of 0.05 for a group size of 40. Based on the findings of Myrick et al., (2008) for the difference between the activation of the ventral striatum for placebo and naltrexone groups a power of 0.88 was seen for an effect size of 0.7 for a group size of 40.

**Safety Analysis:** For safety, subjects will be assessed as having had any serious adverse event during the treatment period or not, and additional analyses will be done by separate types of adverse events. Tolerability will be assessed as a subject being able to continue on the study drug for the entire study duration without requiring discontinuation. The safety and tolerability of the study medications will be first assessed using contingency tables and chi-square tests. Fisher's exact test will be employed for rare adverse events. The chi-square analysis will be followed by logistic regression analyses, adjusting for the stratification factor. Time to drug discontinuation for serious adverse events and time to withdrawal from the study for any reason will be assessed using Kaplan-Meier survival curves and compared between study treatments using the log rank test. Poisson regression will be used to evaluate the rate of serious adverse events by arm stratified by the time periods of dosage escalation, dosage maintenance, and dosage taper.

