#### Potential side effects of Zonisamide

The most common adverse reactions associated with ZON administration in seizure patients include: somnolence (17%), dizziness (13%), and anorexia (13%). Less common adverse effects include: agitation (9%), irritability (9%), depression (6%), speech abnormalities (5%), confusion (6%), difficulty with concentration (6%), difficulty with memory (6%), fatigue (8%), insomnia (6%), nausea (9%), and headache (10%). In some patients, ZON can contribute to problems with concentration, attention, memory, mood, thinking, speech, or language. ZON may produce urinary lithiasis [Kubota et al., 2000]. The incidence of this is reported to be 1.9% in clinical trials in the United States and 0.2% in Japanese clinical trials. The risk of urinary stone formation may be higher in dehydrated and bedridden patients.

Acute myopia and secondary angle closure glaucoma have been reported in patients receiving ZON. Symptoms in reported cases have included acute onset of decreased visual acuity and/or ocular pain. Symptoms typically occur within one month after initiating ZON therapy.

Zonisimaide can cause metabolic acidosis, which results in high levels of acid in the body. If untreated, metabolic acidosis can lead to kidney stones or soft bones. Kidney stones can also occur while taking ZON in the absence of metabolic acidosis. The rate of occurrence for kidney stones is 28.7 per 1000 patient-years of exposure in the first six months, 62.6 per 1000 patient-years of exposure between 6 and 12 months, and 24.3 per 1000 patient years of exposure after 12 months of use (Food & Drug Administration (FDA), 2020).

Other rare but potentially life threatening side effects include allergic reactions that may affect different parts of the body, cause blood cell changes such as reduced white blood cells counts, or lead to a serious skin rash such as Stevens-Johnson Syndrome (SJS) or Toxic Epidermal Necrolysis (TEN). SJS and TEN are two forms of the same life-threatening skin disease that cause rash, skin peeling, and sores on the mucous membranes.

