**Describe the potential benefits to society and/or others related to the study**

This study promises to provide important information about the relative efficacy and safety of a novel treatment strategy to improve outcome for patients with AUD.

The results of this study should provide information on the neurobehavioral mechanisms through which Zonisamide may act to facilitate the reduction of drinking in AUD. These findings may be of value in helping to differentiate individuals with AUD who fail to respond to the effects of Zonisamide administration on subjects from those who do not based on their reactivity on alcohol cue tasks. This would provide a basis for identifying subjects who would expect to benefit from treatment from Zonisamide. It could also be of value in the screening of newly synthesized broad spectrum anticonvulsant medications that are structurally related to Zonisamide for their potential efficacy as medications for the treatment of AUD.

Also, the results of this study should provide further evidence regarding the usefulness of Take Control computerized alcohol reduction and medication compliance program for use in alcohol treatment clinical trials. Information obtained regarding the neurobehavioral mechanisms that mediate Zonisamide's effects on alcohol consumption will provide a basis for determining which patients might be most responsive to Zonisamide's therapeutic effects on AUD. They, also, may help in the development of procedures for assessing whether newly synthesized drugs that chemically related to Zonisamide may be of potential use in the treatment of AUD.

A potential benefit of undergoing MRI scans is the discovery of previously undiagnosed structural brain abnormalities. If there are possible brain abnormalities, MRI examinations and results can be forwarded to Primary Care Physicians if subjects complete a Medical Records Release Form.

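### Safety by adverse-event type rests on chi-square or Fisher tests at 50 per arm, with no risk difference, interval or upper bound specified for any harm

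*Combined protocol and SAP*

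**What the plan says.** The Safety Analysis paragraph (Combined protocol and SAP, Section L) classifies each participant as having or not having a serious adverse event (SAE), adds analyses by type of adverse event, and defines tolerability as staying on study drug throughout. The first step is: "The safety and tolerability of the study medications will be first assessed using contingency tables and chi-square tests". Then: "Fisher's exact test will be employed for rare adverse events". No threshold for rare is given. Logistic regression follows the chi-square analysis. Kaplan-Meier curves with a log-rank test cover time to discontinuation for SAEs and time to withdrawal for any reason. Poisson regression covers SAE rates by arm and dosing period.

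Neither that paragraph nor any other section commits to a risk difference, confidence interval, upper bound or detectable rate for a harm. The Power Analysis paragraph gives power only for drinking, for errors of commission on the CPT and for ventral striatum activation.

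Section M (Potential side effects of Zonisamide) lists 14 reactions at 5% to 17% in seizure patients, 11 of them at 5% to 10%, and urinary stones at 1.9% in US trials. It gives no placebo rates. Section N expects the trial to give "important information about the relative efficacy and safety of a novel treatment strategy". Section R has the DSMB receive unblinded numbers and rates of adverse events by arm.

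**The concern.** A test of no difference answers a useful safety question only if it has a fair chance of detecting a real excess. At 50 per arm that chance is small for most of the side effects the protocol itself lists. A p-value above 0.05 then reflects mainly the sample size and the event rate. A reader of the results could take it as reassurance, because the plan calls for no estimate that would show how large an excess remains compatible with the data.

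The gap matters most for non-serious events by type. The time-to-event and Poisson analyses address SAEs, discontinuation for SAEs and withdrawal. For the other adverse-event types, the chi-square or Fisher test and the logistic model after it are all that is planned.

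**Working it through.** **Inputs.** 50 randomised per arm and 40 expected at week 12 ("Consequently, we will randomize 50 subjects per group to reach a target of 40 subjects in week 12 of the present study"). Zonisamide rates come from Section M. Assumed, because the documents do not give them: a two-sided 0.05 level for safety tests, and all placebo rates.

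**The plan's own figures.** The statement is: "A power value of 0.9 was found for a group size of 40, with alpha=0.05, and with an effect size of 0.74". With d√(n/2) = 0.74 × √20 = 3.31, power is Φ(3.31 − 1.96) = 0.91, or 0.905 by noncentral t, which agrees. For d = 0.70 the result is 0.88 (0.87 by t), against a stated 0.88. The dropout adjustment is 40/(1 − 0.20) = 50. These figures reproduce, but none concerns safety.

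**Smallest significant split against zero placebo events.**
- Fisher, a versus 0 events: p = 2·C(50,a)/C(100,a). This is 0.056 for a = 5 and 0.027 for a = 6, so at least 6/50 (12%) is needed.
- Uncorrected chi-square: χ² = (a/50)²/[p̄(1 − p̄)(2/50)] with p̄ = a/100. For a = 3, χ² = 3.09 and p = 0.079. For a = 4, χ² = 0.0064/0.001536 = 4.17 and p = 0.041. So 4/50 (8%) is enough.

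**Miss rates.** The probability of p>0.05 is summed over all pairs of counts (x, y), weighting each by Bin(x; 50, zonisamide rate) × Bin(y; 50, placebo rate).

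| Zonisamide rate | Placebo 0%: chi-square | Placebo 0%: Fisher | Placebo half: chi-square | Placebo half: Fisher |
|---|---|---|---|---|
| 17% | 2% | 13% | 74% | 85% |
| 13% | 10% | 35% | 81% | 90% |
| 10% | 25% | 62% | 85% | 94% |
| 9% | 33% | 71% | 87% | 95% |
| 8% | 43% | 79% | 88% | 96% |
| 6% | 65% | 92% | 91% | 98% |
| 5% | 76% | 96% | 93% | 99% |

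Over the 15 listed harms (14 reactions plus stones), the expected number reaching significance is:

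| Assumed placebo rate | Chi-square | Fisher |
|---|---|---|
| 0% | 8.1 | 4.1 |
| 1% | 5.9 | 3.0 |
| Half the zonisamide rate | 1.8 | 0.7 |

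**Tolerability as a yes/no outcome (rates assumed).** Discontinuation of 20% versus 10% is missed 70% of the time by chi-square and 81% by Fisher. For 30% versus 20% the figures are 79% and 84%. The planned log-rank analyses of withdrawal and of discontinuation for SAEs are separate from this comparison.

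**What an interval would show.**
- 3/50 versus 0/50: Fisher p = 0.24. The Wilson limits are 2.1% to 16.2% and 0% to 7.1%. The Newcombe lower limit is 6.0 − √[(6.0 − 2.1)² + 7.1²] = −2.1 points, and the upper limit is 6.0 + (16.2 − 6.0) = +16.2 points.
- 8/50 versus 3/50: p = 0.20. The difference is +10.0 points (−2.8 to +23.1).
- 0/50 in one arm: the exact two-sided 95% upper limit is 1 − 0.025^(1/50) = 7.1%.

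**The case against.** Several stronger readings are tempting, and the documents do not support them.

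- **That the plan will treat p>0.05 as safe.** It never says so, and the Section G hypotheses include none on safety. Section N promises information, not a finding of comparable safety. Contingency tables by arm already give counts and rates.
- **That most listed harms would be missed whichever test is used.** This fails for uncorrected chi-square at a 0% placebo rate, where 8 of 15 harms have more than 50% power. Chi-square is the plan's first-line test. Expected counts in that scenario are at most (8.5 + 0)/2 = 4.25 per arm, so such events might well go to Fisher, but with no threshold for rare this cannot be assumed. A 0% placebo rate is itself unlikely for nausea, agitation or sleeplessness, which Section M also lists as alcohol-withdrawal symptoms.
- **That safety rests on 2×2 tests alone.** Kaplan-Meier, log-rank and Poisson analyses are planned, and the DSMB sees adverse-event rates by arm.
- **That the logistic model is useless.** Its odds ratio has no finite estimate only when an arm has zero events (or all participants have one). Under the half-rate assumption, zero placebo events in 50 has probability 0.97^50 = 22% for a 6% harm, 0.95^50 = 8% for a 10% harm and 0.915^50 = 1% for a 17% harm. Otherwise the model can give an interval, though the plan does not commit to reporting one.

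It is also fair to say that an interval adds no information to the data: imprecision comes from sample size and event rates. What the interval does is make that imprecision visible, which a p-value alone does not.

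**Conclusion.** The point holds as a gap in how harms will be judged. The plan makes significance tests the first basis for safety and tolerability and specifies no effect estimate or bound. For adverse-event types, those tests have low power at the 5% to 10% rates under most plausible placebo rates: with half-rate placebo, a 5% to 10% harm is missed 85% to 93% of the time by chi-square and 94% to 99% by Fisher. In the 0% best case, chi-square misses a 10% harm 25% of the time and a 5% harm 76%.

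These sizes rest on assumed placebo rates, a two-sided 0.05 level, all 50 per arm being evaluable, and rates from seizure patients that may not carry over to alcohol use disorder. The absence of any specified interval or bound does not depend on those assumptions. This is a worthwhile, inexpensive improvement. It does not show that the trial will draw a wrong safety conclusion.

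**What to change.** In the Safety Analysis paragraph:

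1. For SAEs, each adverse-event type and discontinuation, report counts by arm and the risk difference (zonisamide minus placebo) with a Newcombe or exact 95% interval. Add an exact upper bound when an arm has no events.
2. State that p>0.05 will not be read as evidence of no excess harm, and that any safety statement will say what excess the interval leaves open.
3. Keep the planned chi-square and Fisher tests as flags, and keep the Kaplan-Meier, log-rank and Poisson analyses as they are.
4. Use Firth or exact logistic regression where an arm has zero events.

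No margin, larger sample or change in data collection is needed. The cost is a few sentences, a little more table output and a more modest safety statement.

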*Note:* Following randomization, treatment will be discontinued under the authority of the study physician if there is evidence of metabolic acidosis, acute renal injury (>threefold increase in serum creatinine levels from baseline) or a significant change in liver function (AST or ALT > 3X UNL for more than two weeks).

- 5) History of anticonvulsant-induced rash
- 6) Currently taking:
  - a. acamprosate, naltrexone, topiramate, disulfiram, or benzodiazepines
  - b. a medication that is a moderate or major inducer of cytochrome P450 3A4 enzymes
  - c. an amphetamine or other psychomotor stimulant
  - d. opioids or have been treated chronically with opioids
  - e. antipsychotic agents, anticonvulsants, or sedative hypnotics
  - f. drugs with “sulfa” moiety (e.g. sulfonamides, sulfonylureas, carbonic anhydrase inhibitors, thiazides, and loop diuretics), except ethacrynic acid
- 7) Previously received ZON for the treatment of an AUD
- 8) Known allergy to sulfonamides
- 9) Implantation of anything containing magnetically sensitive material including metal plates, aneurysm clips, and cardiac pacemakers, stents; history of sheet metal work, claustrophobia
- 10) Non-English speakers
- 11) Women who are trying to become pregnant, pregnant women or women who are lactating (breastfeeding)

*Note:* Women of child bearing potential (not postmenopausal for at least one year) will only be admitted into this study if they are found to have a negative HCG test during screening and agree to use of an effective means of contraception during the course of the study. Acceptable forms of birth control include one or more of the following: tubal sterilization, partner’s vasectomy, intrauterine device, hormonal birth control pills, hormonal skin patch, hormonal vaginal ring, hormonal under-the-skin implants, and hormone shots. Condoms, considered a less reliable method of birth control, must be paired with one of the above reliable forms.

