#### IV. Biological Assessments

To assess safety-related issues the following will be obtained from subjects: BAC (with alcohol breathalyzer), adverse events, concomitant medication, urine drug screens, urine pregnancy tests for all females of child bearing potential weeks, birth control assessments, blood chemistries and hematology (CMP, CBC, creatinine, LDH, Bicarbonate, liver panel: Bilirubin Direct, Bilirubin Total, ALT, AST, Protin total and Albumin, and Alkaline Phosphate), body weight, Portland Neurotoxicity Scale, Pill Count Compliance, and GGT (as putative biomarker of alcohol use). We will be collecting 1-2 mL of blood from each participant for both the screening session and session 4. We will be collecting 1.5-3 mL of blood from each participant at the screening session and roughly every other week during the acute treatment phase. Overall, we will be collecting between 6.5-13 mL of blood per participant over the duration of their time in the study. The total amount of blood to be drawn overall for the study will therefore be 650-1,300 mL. The Phosphatidylethanol Alcohol Test (PEth) is a blood test that is used to detect prolonged or heavy alcohol consumption within the past 2-3 weeks. The Ethyl Glucuronide (EtG) test indicates the level of ethanol in urine up to 80 hours after ingestion. Zonisamide (the study drug) will be tested for on study week 8. This test will determine levels of Zonisamide in each participant to ensure that they are metabolizing the medication properly. Assessments will be obtained on the first day of study medication administration in the first treatment week and following the schedule appearing in Table 1, thereafter.

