### Alcohol Withdrawal

Subjects may experience symptoms associated with alcohol withdrawal. Approximately 1.2% (1 out of 85) of subjects in a recent alcohol dependence treatment study (Interdisciplinary Study of Two Novel Anticonvulsants in Alcoholism, 2013), in which anticonvulsants were being evaluated, had experienced withdrawal symptoms severe enough to require in-patient detoxification. Subjects requiring treatment for withdrawal in the present study will be referred for detoxification at other treatment sites and will not be readmitted into this study. The risk of

severe withdrawal is minimized by the requirement that subjects must be sober when they provide informed consent.

Persons drinking at the level required for entry may experience moderate to severe withdrawal symptoms if they stop drinking abruptly or if they attempt to taper their drinking, including shakes or tremors, chills, nausea and/or vomiting, agitation, sleeplessness, seizures, and delirium (disorientation, altered sensorium, and hallucinations).

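### The only cause-specific drug-discontinuation curve and the only event-rate model count serious adverse events alone, so stops for non-serious effects are compared only when pooled with every other reason

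*Combined protocol and SAP*

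**What the plan says.** The safety plan is one paragraph in Section L (Safety Analysis), after the power analysis. It names these between-arm analyses:

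- A log-rank comparison of "Time to drug discontinuation for serious adverse events".
- A second curve: "time to withdrawal from the study for any reason will be assessed using Kaplan-Meier survival curves", also with a log-rank test.
- A rate model: "Poisson regression will be used to evaluate the rate of serious adverse events by arm stratified by the time periods" of escalation, maintenance and taper.
- A binary outcome: "Tolerability will be assessed as a subject being able to continue on the study drug for the entire study duration without requiring discontinuation".
- For that outcome and for serious events: "The safety and tolerability of the study medications will be first assessed using contingency tables and chi-square tests", then adjusted logistic regression. Fisher's exact test is held for rare events.
- Further analyses by type of adverse event, not limited to serious ones.

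Three other places bear on this. The note to exclusion 4 in Section I (Eligibility Criteria) says "treatment will be discontinued under the authority of the study physician if there is evidence of metabolic acidosis", and adds creatinine and liver-enzyme criteria; Section M (Zonisamide) repeats the rule. Section L (Interventions, Zonisamide) lets patients who must stop medication stay in the study for assessments. Section R (Monitoring of Safety Data by the DSMB) uses the FDA definition of a serious event, extended to any event that an investigator or the DSMB judges a significant hazard.

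**The concern.** The plan's laboratory stop criteria describe findings that need not be serious events. The common reactions listed in Section M (somnolence 17%, dizziness 13%, anorexia 13%, all in seizure patients) are usually not serious either. If stops for such effects differ between arms, the analysis meant to show discontinuation by cause and over time will not count them.

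What it does count may be very few events. A curve or rate ratio resting on one or two events has an interval so wide that it excludes almost nothing, yet it can be reported as showing no safety difference.

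**Working it through.** **Plan's own figure.** The only power figures concern efficacy and mechanism. For drinks per day, 40 per group, d = 0.74 and two-sided alpha 0.05 give power 0.905 by the t-test (stated: 0.9). Inflating for 20% dropout, 40 / 0.8 = 50 per arm. Both reproduce. No expected number of serious events, discontinuation rate or safety power is stated.

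**Step 1: where a non-serious stop is counted.** Take a patient whose drug is stopped for metabolic acidosis, where the event is not classed as serious and the patient stays for assessments.

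| Planned analysis | Is this stop an event? |
|---|---|
| Time to drug discontinuation for serious events | No |
| Time to study withdrawal, any reason | No, the patient has not withdrawn |
| Poisson rate of serious events | No |
| Analyses by adverse event type | The adverse event may count; the stop does not |
| Binary tolerability | Yes, pooled with all other reasons |

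**Step 2: how many serious events.** Section M (Alcohol Withdrawal) offers one anchor: "Approximately 1.2% (1 out of 85) of subjects" in an earlier trial needed inpatient detoxification. 1/85 = 1.18%, exact 95% CI 0.03% to 6.4%. This is one event type, so using it for all serious events is an assumption. A second anchor is the kidney-stone rate in Section M, 28.7 per 1000 patient-years in the first six months: 50 × 12/52 = 11.5 patient-years, × 0.0287 = 0.33 cases expected in the zonisamide arm over 12 weeks, not all serious.

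With risk p equal in both arms and 50 per arm, the expected number per arm is 50p, and P(at least one arm has none) = 1 − [1 − (1 − p)^50]².

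| p (assumed) | Expected per arm | (1 − p)^50 | P(at least one arm has none) |
|---|---|---|---|
| 1.2% (1/85) | 0.6 | 0.553 | 80% |
| 2% | 1 | 0.364 | 60% |
| 4% | 2 | 0.130 | 24% |
| 6% | 3 | 0.045 | 9% |

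Drug stops because of a serious event cannot exceed the number of subjects with one.

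**Step 3: what such counts can show.** Log-rank power by Schoenfeld's formula is Φ(√d × |ln HR| / 2 − 1.96) for d events. At HR 3 it is 0.08 with 1 event, 0.12 with 2, 0.23 with 5 and 0.41 with 10. For 80% power, d = 4 × (1.96 + 0.84)² / (ln 3)², or 27 events.

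Exact conditional 95% intervals for the rate ratio at equal exposure are 0.013 to 78 for 1 v 1 events, 0.10 to 118 for 2 v 1, and 0.19 to infinity for 2 v 0. Fisher's test at 50 per arm needs a 6 v 0 split (p = 0.027); 5 v 0 gives p = 0.056.

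**Step 4: what the wider outcome can show.** The documents give no rate of stopping for adverse events, so all rates here are assumed. Exact Fisher power at 50 per arm:

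| Placebo v zonisamide | Expected events | Power |
|---|---|---|
| 2% v 10% | 6 | 0.19 |
| 4% v 16% | 10 | 0.37 |
| 4% v 20% | 12 | 0.59 |
| 5% v 25% | 15 | 0.75 |

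**The case against.** The strongest reply is that the same paragraph already covers the ground. A laboratory stop counts as a failure in the tolerability comparison, adverse events are analysed by type, and withdrawal for any reason has its own curve. Section R also gives the DSMB yearly unblinded adverse-event rates and reasons for dropout by arm. All of this is correct. A reader might infer that non-serious stops are never compared between arms; the documents do not support that. What remains is that the one planned test containing every such stop cannot separate cause or timing. The DSMB summaries are descriptive monitoring, and they report dropout, which need not include every drug stop.

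A reader might also infer that the trial expects almost no serious events and that the models will fail. No serious-event rate is stated, the 1/85 figure covers detoxification only, and the extended definition in Section R could bring some laboratory stops in as serious. At 4% and 6%, both arms have at least one event with probability 76% and 91%.

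Nor do empty arm-by-period cells settle the matter. The plan's wording can mean an arm effect adjusted for period, and that estimate is finite once each arm has an event. With 2 v 1 events and three of six cells empty, a main-effects fit gives a log rate ratio of −0.69 with SE 1.22, which equals √(1/2 + 1/1): very imprecise, but not missing.

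Finally, Fisher's exact test is already allowed for rare events. That protects the crude table, not the log-rank, Poisson or adjusted logistic results.

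**Conclusion.** The point holds as a gap in the safety analysis that is cheap to close. The only discontinuation analysis by cause and the only rate model are confined to serious events, and a stop for a non-serious effect can be an event in neither planned curve. It appears only in an all-cause binary comparison.

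Under an assumed serious-event risk of 1.2% to 6%, equal in both arms, 0.6 to 3 subjects per arm are expected. The serious-event results would then be very imprecise throughout, and often not estimable only towards 1-2%, where one arm or both have no event in 60% to 80% of trials. The structural part does not depend on these rates: it follows from the plan's definitions and from the permission to stay in the study after stopping the drug.

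Two nearby matters are missing detail and carry no weight here: the logistic model adjusts for a single stratification factor although the Randomization section names four variables, and the Portland Neurotoxicity Scale has no named comparison.

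**What to change.** Define the time-to-event safety outcome as study-drug discontinuation for any adverse event, including the laboratory-triggered stops, whether or not classed as serious and whether or not the patient stays in the study. Treat discontinuation for other reasons as a competing event and report cumulative incidence by arm. Keep the serious-event curve as a listing or supportive display, and leave the all-cause tolerability and withdrawal comparisons as they are.

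For serious events, estimate the arm effect with an exact conditional or Firth-penalised method, stratified by dosing period where the counts allow, in place of the ordinary Poisson and adjusted logistic models. Report the interval with the counts, so that a sparse result is not read as evidence of equal safety.

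The cost is plan wording and a little programming. Adverse events, pill counts and laboratory tests are already scheduled in Table 1; the reason for each drug stop must also be recorded. The change makes the comparison more informative but does not guarantee power: even at an assumed 4% v 20%, Fisher power is only 0.59.
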